## 5.7 Withdrawal of Subjects

Eligibility for rewards both financial and non-financial will be stated in the informed consent.

**5.7.a. Active withdraw.** Any participant may at any time notify the Principal Investigator or research coordinator(s) that they no longer wish to participate in the study and they will be considered withdrawn and will no longer participate in study procedures or activities. We will make every attempt to have a final study visit with the participant, ideally lining up with one of the three scheduled follow-up visits. For example, if a subject expresses that they'd like to withdraw from the study at week 11, we will halt all study procedures but will ask the participant if they could still come in for their week 16 visit and complete the interview. If they are not interested in coming in for a final study visit, and if they still have their Blipcare scale and/or Connect device, we will mail them a pre-paid box to return those items and they will be withdrawn immediately. If a final study visit is possible a final weight and survey will be recorded. At this point in time, depending on the arm of the study the participant was randomized to, they will be told the total amount they can expect to receive in the mail, or they will be notified of the non-financial reward(s) they have earned.

**5.7.b. Passive withdraw.** This study has multiple time-sensitive in person meetings, portal and phone communications. If we do not hear from a participant within 3 days of a missed in-person meeting we will call them and reschedule (Appendix O). If we do not reach them, we will make up to three total attempts to contact them. If the participant misses four weekly weight entries in a row we will make up to three attempts to contact them for every four week stretch they miss. We will make up to 30 total attempts to reach them via phone, voicemail, postcard and letter (Appendices E, O, Q and P), over the course of 19 weeks if we do not hear from them after the baseline appointment.

For each week the participant doesn't respond after the initial week a total of 3 attempts will be made to contact participants for each occurrence of not responding to study staff inquiries. Inquiries include reminder text messages, emails, phone calls from study staff and postcards.

If the participant doesn't complete the baseline survey within four weeks of their baseline study visit, they will be withdrawn from the study. Prior to being withdrawn, we will make up to three attempts to contact them. Depending on what study arm the participant is in, the participant will be compensated for their participation up to the point where they stopped participating.

**5.8.c. Medical withdraw.** If a participant loses more than 10 pounds in one week the research staff will discuss the participants' weight loss strategy with them. The physician researchers, [name] [name] or [name] will also review their chart to determine if there is medical condition that would contra-indicate further participation. If the participant is engaging in unhealthy methods of weight loss they will be counseled against these methods, referred to their primary care provider, and the MOVE! workbook methodologies will be reiterated. The participants will also be told that if a clinician determines their weight loss exceeds healthy limits, they may be withdrawn from the study. If the participant discloses their pregnancy or the study team finds out they are pregnant they will not be able to continue in the study. If this occurs the same withdraw procedures will be followed for active withdraw. Participants will be compensated for all activities earned to the date of withdraw as outlined in the informed consent document.

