### 3.0 Objectives

The proposed study is based on the hypothesis that the regain found in prior reward studies was due in part to their use of financial rewards, and financial rewards may make patients especially susceptible to regain. Experiments in behavioral economics have found that when participants were provided financial rewards for performing a task, their behavior toward the task was defined by reciprocity—the effort the participants gave was proportional to the amount of money that they were given. When participants were given non-financial rewards, they exhibited no reciprocity—the effort was consistently high and did not vary with the quantity of the non-financial reward. These findings have been confirmed in field studies, and experiments using functional MRIs: money as a reward makes us think and behave differently. By using financial rewards, prior trials may have invoked money-market norms of reciprocity, such that patients' efforts toward weight loss were high when rewards were offered, and reduced when they were discontinued. We hypothesize that non-financial rewards, such as tickets to a Seattle Mariners baseball game, will not invoke reciprocity or the consequent weight regain. We also hypothesize that the affective or emotional characteristics of non-financial rewards can make them more powerful than financial rewards. A patient's thoughts about receiving a non-financial reward, such as tickets to baseball game, can create a positive emotional reaction that can be more salient than the cash value of the reward.

The goal of this study is to test, through a randomized trial, the effectiveness of providing obese Veterans with financial or non-financial rewards for losing 1 lb. per week over 16 weeks. The primary outcome is weight loss at 32 weeks—16 weeks after the discontinuation of the rewards. Secondary outcomes include weight loss at 16 weeks and 12 months. The specific aims are outlined below.

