### 5.6.a. Data Analysis

All data will be analyzed at VA Puget Sound Health Care System by one of the data analysts and/or investigators.

We will use an intent to treat analysis. To test each hypothesis we will estimate an equation of the form

$\Delta Y_{it} = \beta_0 + \beta_1 Weight_{i0} + \beta_2 M_i + \beta_3 F_i + u_i$  (1) where  $\Delta Y_i$  is change in weight from baseline to follow-up time t

for patient i;  $Weight_{i0}$  is baseline weight for patient i; F is the financial rewards (arm 2); M is an indicator for assignment to non-financial rewards (arm 3); and u is a random error. To gain a small amount of efficiency we can also estimate (1) using repeated measures of change in weight from baseline to the three follow-up measures (16 weeks, 32 weeks and 12 months) using GEE models of the same form as equation (1), except with dummy variables for follow-up periods and interactions between these variables and the treatment group dummies.

Hypothesis 1a implies a test of superiority and will be assessed using two-sided tests of  $\beta_2 = 0$  for non-financial rewards, and  $\beta_3 = 0$  for financial rewards. Large positive or negative values of  $\beta_2$  and  $\beta_3$  are evidence against the null hypothesis of no difference between reward and non-reward groups.

Hypothesis 1b implies a non-inferiority test. We will reject the hypothesis that non-financial rewards are inferior to financial rewards if  $\beta_2$  is statistically significantly greater than zero (i.e., there was statistically significantly more weight loss in the non-financial reward arm than in usual care) and if  $(\beta_3 - \beta_2) < 2.5 kg$ , where  $(\beta_3 - \beta_2)$  is the adjusted difference in mean weight loss between the financial and non-financial reward arms, and 2.5 kg is half the 5 kg weight loss assumed to be clinically significant. Although there are no defined rules for choosing a range of indifference for a non-inferiority test, researchers often use half the minimum clinically significant amount. Values of  $(\beta_3 - \beta_2)$  that are statistically significantly larger than 2.5 kg are evidence against the hypothesis that non-financial rewards are not inferior to financial rewards.

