Hypothesis 1c implies a test of superiority and will be assessed using two-sided tests of  $(\beta_3 = \beta_2)$  in comparisons of weight change from week 16 to week 32 and 12 months, respectively. We will use weight change at week 16 in place of weight at baseline in equation 1, such that differences in weight regain between treatment arms will be adjusted for weight lost over weeks 1-16.

Because all secondary outcomes are continuous variables, a similar equation will be used to assess changes in secondary outcomes. These analyses explore how rewards affect constructs that are believed to mediate the effect of rewards on weight loss.

Missing weight measures will be imputed using data from patients' medical records for routine medical visits and methods developed and tested via simulation by [name] et al. These methods involve estimating longitudinal mixed-effects linear models of weight collected both through the trial and at routine clinic visits as a function of polynomials of time since enrollment, with random components for patient intercept and time, and using the predicted values from this model for any post intervention day as an estimate of what the patient's weight would have been on that day if he/she kept their follow-up appointment.

We assumed a standard deviation of 11.0 lbs. for weight loss based on the results of the JAMA (2008) and JGIM (2011) trials that were conducted in the VA and demonstrated statistically significant differences in

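### For participants who actively withdraw before week 16, the section 5.7.a example leads to one visit at week 16 and no week-32 weight, leaving the primary outcome to imputation

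*Combined protocol and SAP*

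**What the plan says.** Section 3.0 sets the endpoint: "The primary outcome is weight loss at 32 weeks", which is 16 weeks after rewards end. Section 5.6.a states the principle: "We will use an intent to treat analysis".

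Under section 5.7.a, participants who say they wish to stop are handled as follows: "they will be considered withdrawn and will no longer participate in study procedures or activities". Staff then seek one more contact: "We will make every attempt to have a final study visit with the participant, ideally lining up with one of the three scheduled follow-up visits". The single example is a withdrawal at week 11, after which staff "ask the participant if they could still come in for their week 16 visit" and complete the interview. Those who do not want a final visit return any study devices by mail, and "they will be withdrawn immediately".

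Section 5.6.a provides for gaps: "Missing weight measures will be imputed using data from" routine medical visits. The method is a longitudinal mixed model fitted to trial and clinic weights. It uses polynomials in time and patient-level random effects, and its prediction stands in for the missed measurement.

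**The concern.** Stopping the programme and leaving outcome follow-up are different events, and section 5.7.a treats them as one. Intent to treat needs the week-32 weight whether or not a participant still enters weights or can earn rewards. Staff who follow the example would collect a secondary time point and not seek the primary one.

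Week 16 is a weak stand-in for week 32. The central hypothesis is about regain after rewards stop, and that interval begins at week 16. Hypothesis 1c compares change from week 16 to week 32 and to month 12, so a lone week-16 visit gives no measured change over either period.

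Withdrawal may also be informative. Section 5.1.a removes rewards once the goal would need more than 4 lb a week, a possible reason to disengage that exists only in the reward arms. It also plans to ask people who withdraw why the study did not work for them. Withdrawal related to both arm and weight course is plausible, although the documents give no data on it.

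**Working it through.** **What section 5.7.a yields, by time of active withdrawal**

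| Withdrawal | Final visit under the text | Study-measured week-32 weight |
|---|---|---|
| Before week 16, handled as in the example | Week 16 | Not sought |
| Weeks 17 to 31 | Week 32 or month 12; the text does not rank them | Possible, not required |
| After week 32 | Month 12 | The week-32 visit time has already passed |
| Any time, final visit declined | None | Not sought if before week 32 |

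The gap is clearest in the first row.

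**Reproducing the plan's figures**

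Inputs from section 5.6.a: SD 11.0 lb, two-sided alpha 0.025, 80% power, target difference 11 lb, 20% loss to follow-up, arms of 80, 100 and 100. The normal quantiles are 2.241 and 0.842, which sum to 3.083.

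- n per arm = 2 × (11/11)² × 3.083² = 19.0, or 20 after rounding up. The t-test solution is 20.3, which rounds up to the stated 21.
- With 20% loss: 21/0.8 = 26.25, so 27, against 28 stated.
- Detectable difference at 80 vs 100: 11 × √(1/80 + 1/100) × 3.083 = 1.65 × 3.083 = 5.09 lb (t-based 5.12). The stated 5.1 lb therefore assumes every enrolled participant has a week-32 value.

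**Effect of missing week-32 weights, complete cases only**

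| Missing | n (control vs reward) | Detectable difference, normal (t-based) | Power for 5.1 lb |
|---|---|---|---|
| 0% | 80 vs 100 | 5.09 (5.12) lb | 0.80 |
| 10% | 72 vs 90 | 5.36 (5.40) lb | 0.755 |
| 20% | 64 vs 80 | 5.69 (5.74) lb | 0.70 |
| 30% | 56 vs 70 | 6.08 (6.14) lb | 0.635 |

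Only the 20% is the plan's figure; 10% and 30% are an assumed range. Power for 11 lb stays above 0.99 throughout. If asking for week 32 recovered half of a 20% loss, the detectable difference would fall from about 5.7 to 5.4 lb.

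**Illustrative bias**

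If the imputation error is the same in both arms, bias in the contrast = (difference in withdrawal proportion) × (mean imputation error). Neither input is in the documents.

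- Assumed 10 points and 5 lb: 0.10 × 5 = 0.5 lb.
- Low end, 5 points and 3 lb: 0.05 × 3 = 0.15 lb.
- High end, 20 points and 10 lb: 0.20 × 10 = 2.0 lb.

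If the imputation error differs by arm, bias can arise even with equal withdrawal rates.

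**The case against.** A reader might infer that every withdrawer is sent to the next scheduled visit. The text does not say so: the final visit is sought "ideally lining up with one of the three scheduled follow-up visits", and week 16 appears only as an example. A reader might also infer that the week-32 outcome is lost and the intent-to-treat analysis broken. Section 5.6.a does not support that either. It imputes missing weights from trial and chart data, participants are active primary care patients who may well have chart weights, and a week-16 weight from a withdrawer would inform the model. What is missing is the study measurement. Both objections stand.

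The imputation is still not equivalent to a measurement. As described it has no treatment-arm term, so predictions may shrink toward a common course. It depends on a chart weight existing near week 32. The plan does not say whether chart weights after withdrawal will be used, and it describes no sensitivity analysis for informative withdrawal.

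The magnitude is also open to challenge. The 20% is loss from all causes, while section 5.7.a covers active withdrawers, plus pregnancy withdrawals by reference. Non-responders fall under section 5.7.b, with up to 30 contact attempts, and this change would not reach them. The precision figures are complete-case, whereas the plan imputes. These points stand, and they make the figures upper-end illustrations.

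Week 16 has its own uses: it is the time point for hypothesis 1b and the covariate for 1c. Someone leaving at week 11 may accept a visit 5 weeks away more readily than one 21 weeks away. This argues against replacing the week-16 request, but not against adding to it.

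Reach is limited. Section 5.1.c reports 274 enrolled and recruitment stopped, so only later withdrawals before week 32 can benefit. The consent form and contact appendices are not in the text available, so whether they cover follow-up after withdrawal cannot be judged.

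**Conclusion.** The point holds in a narrow form. Section 5.7.a merges stopping the programme with leaving outcome follow-up, and its one example leads an early active withdrawer to week 16 only. For those participants no study-measured week-32 weight is sought, and the primary outcome rests on a model prediction. This is a stated procedure that gives weaker data than an easy alternative, but it does not invalidate the analysis.

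The size is uncertain. The move from about 5.7 to 5.4 lb would need active withdrawal to account for at least half of the 20% loss, with enough of those participants agreeing to recover half of the total, and it ignores imputation. The 0.5 lb bias, with an illustrative range of 0.15 to 2.0 lb, rests wholly on assumed inputs. The power for the plan's 11 lb difference is not threatened.

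**What to change.** Amend section 5.7.a so that anyone actively withdrawing before week 32 is asked, separately from stopping study procedures, whether they will give a voluntary week-32 weight. It could be taken in clinic, or by phone with the mode flagged. Keep the existing week-16 request where it applies, and add month 12 for those willing. Change the week-11 example to match. Record as withdrawn from follow-up only those who decline. State whether the request extends to pregnancy withdrawals, which use the same procedure.

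The means already exist: phone visits with the $20 payment (section 5.1.a) and a file marking weights reported by phone (section 5.1.b). The cost is a short protocol change, a small extra contact burden, $20 per visit and possibly minor consent wording. Some participants will decline.

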### 6.3 Safety Review Plan

Study progress and safety will be reviewed monthly (and more frequently if needed). Patient weight loss will be closely monitored and if weight loss occurs at a rate of more than 5 pounds per week, a clinical review will be

completed. An annual report will be compiled and will include a list and summarization of adverse events. In addition, the annual report will address (1) whether adverse event rates are consistent with pre-study assumptions; (2) reason for dropouts from the study; (3) whether all participants met entry criteria; (4) whether continuation of the study is justified on the basis that additional data are needed to accomplish the stated aims of the study; and (5) conditions whereby the study might be terminated prematurely.

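### Withdrawal for excessive weight loss leaves the week-32 and 12-month weights unassured; the likely bias is small and the remedy is cheap

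*Combined protocol and SAP*

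**What the plan says.** Section 3.0 sets the endpoint: "The primary outcome is weight loss at 32 weeks", with 16 weeks and 12 months as secondary times.

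Section 5.8.c (medical withdrawal, printed under 5.7) starts from a rapid loss: "If a participant loses more than 10 pounds in one week the research staff will discuss" the participant's strategy. A physician reviews the chart, and anyone using unhealthy methods is counselled and referred to primary care. Participants are also told that "if a clinician determines their weight loss exceeds healthy limits, they may be withdrawn from the study". The sentence refers to the study, not only to the rewards, and names no arm.

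For active withdrawal, 5.7.a says "they will be considered withdrawn and will no longer participate in study procedures or activities". It adds: "We will make every attempt to have a final study visit with the participant", preferably at one of the three scheduled follow-up visits. Its example is a withdrawal at week 11 followed by a week-16 visit. Section 5.8.c refers back to these procedures, but directly after its sentence on pregnancy.

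On analysis, 5.6.a says "We will use an intent to treat analysis" and "Missing weight measures will be imputed using data from patients' medical records for routine medical visits". The imputation model also uses weights collected in the trial. It lists polynomials in time and random patient terms, and no treatment arm. No sensitivity analysis for outcome-related missingness is described.

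**The concern.** Weight loss is both the ground for this withdrawal and the quantity the trial measures. Staff can end follow-up because of a value closely tied to the primary outcome, and nothing in the text assures a week-32 or 12-month weight afterwards. A week-16 final visit would supply hypothesis 1b but not hypotheses 1a or 1c.

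If such withdrawals fall more often in the reward arms, large losers in those arms are replaced by model predictions, or lost if a prediction cannot be made. The reward-versus-control contrast would then be pulled toward no difference. The protocol itself lists unhealthy behaviour aimed at the study goals as a risk (5.1.b), so the situation was foreseen.

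**Working it through.** **1. The plan's yardstick.** Inputs from 5.6.a: SD 11.0 lb, two-sided alpha 0.025, 80% power, 80 usual care and 100 per reward arm.

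Detectable difference = 11.0 × √(1/80 + 1/100) × (2.241 + 0.842) = 11.0 × 0.15 × 3.083 = 5.09 lb. The plan states 5.1 lb, so it reproduces (with no loss to follow-up).

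**2. Path to a missing weight.** Take 5.7.a's own example: withdrawal at week 11, one visit at week 16, then no further study contact. The week-32 and 12-month weights are missing unless a routine clinic weight exists. If the cross-reference in 5.8.c covers pregnancy only, even the week-16 visit is not promised.

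**3. Which arm?** The documents do not say. As a rough guide, assume normal week-32 losses with SD 11 and the means in 5.6.a: 1.6 lb in usual care and 6.7 lb in each reward arm. Total loss stands in for weekly loss. The expected number beyond a threshold is n × P(Z > (threshold − mean)/11).

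| Loss above | Usual care (80) | Each reward arm (100) | Share in the two reward arms |
|---|---|---|---|
| 20 lb | 3.8 | 11.3 | 86% |
| 25 lb | 1.3 | 4.8 | 88% |
| 30 lb | 0.4 | 1.7 | 90% |

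Allocation alone gives 200/280 = 71%. An excess in the reward arms is plausible, but it rests on the proxy.

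**4. Size if these people were left out (not the planned analysis).** Let p be the share withdrawn, L their true week-32 loss and m the full arm mean. The arm mean falls by p(L − m)/(1 − p). Both p and L are assumptions. For m, Table 1's follow-up row gives 8.1 lb for the raffle arm and 3.1 lb for the lottery arm; the row is labelled as a minimum detectable difference, so these are planning values.

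| p | L | Shift, m = 8.1 | Shift, m = 3.1 |
|---|---|---|---|
| 2% | 20 lb | 0.02 × 11.9/0.98 = 0.24 lb | 0.02 × 16.9/0.98 = 0.34 lb |
| 3% | 25 lb | 0.03 × 16.9/0.97 = 0.52 lb | 0.03 × 21.9/0.97 = 0.68 lb |
| 5% | 30 lb | 0.05 × 21.9/0.95 = 1.15 lb | 0.05 × 26.9/0.95 = 1.42 lb |

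A separate bound removes the top fraction f of one reward arm by week-32 loss and nobody from usual care. The bias is 11 × φ(z)/(1 − f), where z is the upper-f normal quantile. It is 0.54 lb at f = 2% (power 0.80 to 0.72 for a true 5.1 lb difference) and 1.19 lb at f = 5% (power 0.58). If the ground for withdrawal correlates only 0.3 to 0.7 with week-32 loss, these become 0.16-0.38 lb and 0.36-0.84 lb.

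**5. Size under the planned imputation.** An illustrative simulation used a model of the 5.6.a type (cubic time, random intercept and slope) with withdrawal at week 6: 12 trials, 72 withdrawn participants. Mean true week-32 loss was 21.7 lb and mean predicted loss 17.1 lb, a shortfall of 4.6 lb each. At 3% withdrawn, 4.6 × 0.03 = 0.14 lb on the arm mean, and 0.14/5.1 = 2.7% of the detectable difference. The documents give no variance components for this model, so this is an order of magnitude only.

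**6. Review triggers side by side.** Section 5.1.a: staff contact at a loss of 10 lb or more in a week. Section 5.8.c: discussion and chart review above 10 lb in a week. Section 6.3: clinical review "if weight loss occurs at a rate of more than 5 pounds per week". These do not agree on when a clinician looks at the case.

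**The case against.** The strongest reply is that this is a discretionary safety provision. It comes after discussion and chart review, applies to every arm, and will touch few people. All of that stands. A reader might infer that the outcome itself decides who is weighed at week 32. The text does not support that: withdrawal is optional, needs a clinician's judgement, and is tied to current loss rather than the week-32 value.

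A reader might also infer a contradiction with intent to treat. There is none. Ending contact creates missing data, and 5.6.a imputes those data. The weights that prompt withdrawal are largely already recorded, and missingness driven by recorded weights does much less harm to a mixed model than missingness driven by unseen ones. What remains is that a prediction is weaker than a measurement, and that a model without an arm term can pull early extreme losers toward the pooled curve.

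The arm imbalance can be challenged too. Table 1 reports mean losses over months and says nothing about weekly losses above 10 lb. Rewards are for reaching a target, not beating it, and weekly goals are capped at 4 lb (5.1.a). The imbalance is therefore plausible but not shown.

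Finally, it would be wrong to say that care ends at withdrawal. Chart review and, for those using unhealthy methods, referral to primary care are written into 5.8.c, and a final visit is attempted under 5.7.a. None of these assures a week-32 weight.

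**Conclusion.** The point holds as a gap in outcome collection. Withdrawal for excessive loss can leave the week-32 and 12-month weights missing for a reason related to the primary outcome, and the plan does not say these weights will still be sought.

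Under the planned imputation the effect is probably small: about 0.14 lb on a reward-arm mean, assuming 3% withdrawn and the illustrative model. The 0.2-1.2 lb range (2-5% withdrawn, true losses of 20-30 lb, arm mean 8.1 lb) applies only if these people were dropped, which the plan does not propose. In both cases the direction is toward understating the reward effect. The withdrawal rate and its split by arm are assumptions. This is a cheap improvement and not a threat to the primary comparison.

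**What to change.** State in 5.7.a and 5.8.c that participants withdrawn medically for weight loss:

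- are still asked, unless they withdraw consent, for the already planned week-16, week-32 and 1-year weights, in person or by phone (5.1.a already accepts phone weights);
- are analysed as randomised;
- are counted and reported by arm.

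Say also whether the final-visit procedure in 5.7.a covers this type of withdrawal.

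Whether and when to withdraw someone remains the clinicians' decision. The weekly-loss triggers in 5.1.a, 5.8.c and 6.3 must be reconciled by those responsible for them.

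The cost is a sentence or two of text and up to three planned weights for each person affected. The downside is a few extra contacts with people who have been withdrawn. Section 5.1.c records enrolment stopped at 274 as of 3/6/2020, so the wording would help those still in follow-up; the count by arm can be made for everyone.
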